The Chronic Pain Acceptance Questionnaire³ was used to evaluate chronic pain acceptance. This 20-item survey is composed of 2 factors: 1) "activity engagement": engagement in life activities with pain (11 items), and 2) "pain willingness": willingness to experience pain without trying to engage in unhelpful attempts to control it (9 items). Patients were asked to rate the truth of each item as it applied to them (eg, "My life is going well, even though I have chronic pain."). Items are scored on 7-point scale from 0 "never true" to 6 "always true." Higher scores denote greater levels of pain acceptance. Scores on the "activity engagement" subscale range from 0 to 66; scores on the "pain willingness" subscale range from 0 to 54). The Chronic Pain Acceptance Questionnaire has good psychometric properties⁴ as well as evidence of clinical utility.³

The Perceived Efficacy in Patient-Physician Interactions⁵ is a 5-item survey measuring confidence in obtaining medical information and attention to their medical concerns from physicians. Items are scored on a 5-point Likert scale from 1 "not at all confident" to 5 "very confident." The Perceived Efficacy in Patient-Physician Interactions has established validity and reliability in older adults⁵ and patients with osteoarthritis.⁶

Pain and pain interference were evaluated using the 3-item Pain Intensity and Interference With Enjoyment of Life and General Activity (PEG).⁷ Pain intensity was rated on an 11-point numeric rating scale, from 0 "no pain" to 10 "pain as bad as you can imagine." For interference items, patients indicated how much pain interfered with enjoyment of life and with general activity from 0 "does not interfere" to 10 "completely interferes." The PEG total score is the mean of these 3 items, where higher values denote a higher level of pain intensity and interference. The PEG has established reliability and validity in a community and veteran populations with chronic pain and has shown responsiveness to improvement similar to the Brief Pain Inventory.⁸ The PEG was completed as part of the participant's regular clinical care. Assessments within 2 months of the primary PTSM outcome assessment were used for these analyses.

To evaluate satisfaction with pain treatment, participants were asked to choose the number between 0 “extremely dissatisfied” and 10 “extremely satisfied” that best reflected how satisfied they are with the results of their pain treatment, in general.

Study Procedures

Consecutive new patients who attended the UW CPR between April 2016 and March 2017 completed a collection of pain-relevant patient-reported outcome questionnaires using PainTracker to facilitate comprehensive multidimensional pain care. All new patients were asked to complete the online questionnaires 1 week before their scheduled appointment. Those who were scheduled for a follow-up appointment at UW CPR and completed the follow-up PainTracker assessment were presented with a question determining interest in the PTSM study. If patients were interested in learning about the study, they were directed to an online information statement outlining the purposes and procedures of the study and given the opportunity to enroll. Patients who chose to not consent at the time were given the options to decide at a later time or obtain more information regarding the study. These patients were then sent a follow-up e-mail by the research team. Intervention and control subjects were compensated with a \$100 gift card for completion of all outcome measures.

A controlled, sequential, nonrandomized study design was used. During the first 6 months of the enrollment period, assessment procedures for the control group were conducted. The control group received treatment as usual in the CPR, with no restrictions on treatment received, including medications, procedures, and sessions with pain psychology, pain psychiatry, and social work that provided support for pain self-management. While control subjects were being assessed, the Web-based PTSM platform for the intervention phase of the study was developed by the multidisciplinary research team, which included investigators from psychiatry, internal medicine, psychology, nursing, social work, computer science, and graphic design. During the second 6 months of the study enrollment period, patients were enrolled in the intervention group. Control as well as intervention subjects were followed for 6 months. There was no restriction on treatments received in either group. The study procedures were reviewed and approved by the institutional review board at UW.

Intervention

The intervention included exposure, at the patient’s discretion, to a Web-based patient empowerment platform on the basis of ACT principles, as well as phone and text coaching from the research clinicians (trained in nursing and social work, respectively). The flow of the study is shown in [Fig 1](#). The PTSM interactive educational modules covered the following topics: module A: “Introduction to PainTracker” is a brief, non-interactive informational module that was presented to the intervention as well as control patients as an introduction to the first PainTracker assessment. Module B: “What is Pain?,” explained that pain is important, unpredictable, and complex. It emphasized that all pain is real and important. It also emphasized that pain may get better and worse for unclear reasons. It did not focus on the difference between acute and chronic pain. Education on the complexity of pain used concepts of “injury” versus “alarm,” and incorporated some ideas from *Explain Pain* by Butler and Moseley.^{4, 9} Module C: “Life Navigation System,” assisted patients with clarifying values and developing an action plan to improve 1 selected life area (ie, freetime, relationships, health and self-care, or work and education). This module was adapted from a treatment manual written by Vowles and Sorrell¹⁰ and incorporated the Values Bullseye exercise of Lundgren and colleagues.¹¹ Module D: “Get Rhythm,” focused on pacing, mindful breathing, and sleep rhythms. These 3 areas were selected for skill development because they are often core components of behavioral treatments for chronic pain and because of their relevance with the values focus of the intervention. Participants were encouraged to bring some regular rhythm into their lives, particularly as related to engagement in valued living. Module E: “Life Goes On,” the

final module, focused on scheduling value-based activities and managing pain flares over the longer term. These themes were chosen to emphasize the importance of engagement in value-based activities for sustained recovery.¹² Intervention participants were given access to all modules at the outset of the study. They were not forced to complete them on a schedule or in order. The coaches strived to have at least 1 coaching session after the completion of each module. The coaches estimate that patients spent 30 to 40 minutes on each module that they viewed. Module A was especially short and Module B was especially long. Total estimated time for module viewing was 120 to 160 minutes. More precise tracking of viewing time was not possible because of patients' ability to leave the modules open while they attend to other things.

Embedded in each of the interactive modules were open-ended and multiple choice questions and tasks, such as "Of all the things that have happened to you since your pain started, what concerns you the most?" or "Create your own action plan." The responses to these module questions were visible to the coaches and were used to guide and tailor the coaching sessions to the individual patient. Coaching sessions occurred in person (14%), over the phone (85%), or by e-mail and text (1%), on an average of 4 occasions (SD = 1.6) depending on participant preference and availability, with a mean duration of 20 minutes (SD = 8.6, range = 2-50 minutes per session). After each individual coaching session, participants were sent an e-mail summary of the recommendations discussed. At study completion, a final note was sent with a summary of key self-management strategies, and encouragement to continue to incorporate them into daily life.

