Official Study Title: PainTracker Self-Manager: a Web-based Platform to Promote and Track Chronic Pain Self-Management

NCT Number:	NCT03045081
Document Type:	Statistical Analysis Plan
Document Date:	March 21, 2018 (date of most recent submission/review by Journal of Pain)

Statistical Analysis Plan

Data were analyzed using SPSS version 25 (IBM Corp, Armonk, NY).

Descriptive statistics and frequency distributions were calculated for sample characteristics. Independent samples t-tests for continuous variables and χ^2 tests for categorical variables were used to evaluate for differences in demographic and clinical characteristics between the control and intervention groups. Given no statistically significant differences in demographic and clinical characteristics between the groups, the subsequent analyses (described below) did not adjust for any of these characteristics. A *P* value of <.05 was considered statistically significant. For all levels of analyses, adjustments were not made for missing data (i.e., no data imputations were performed).

Generalized estimating equations (GEE) were used to evaluate the effect of the intervention on primary (pain self-efficacy) and secondary (chronic pain acceptance, perceived efficacy in patient-provider interactions, pain intensity and interference, satisfaction with pain treatment) outcomes. GEE is an extension of generalized linear models that allows for the analysis of repeated measures with unknown covariance structure. GEE uses any and all available data that participants provide, even if follow-up data are missing (ie, intent-to-treat analysis). For all models, the main effect of

group and time, and the Group × Time interaction were evaluated. For this pilot study, Wald χ^2 statistics with *P* values <.05 for overall model effects were considered statistically significant. For models with significant Group × Time interactions, the main effects of group or time were not reported. For models with only a significant main effect of time, models were rerun without the interaction term to obtain the more accurate main effect.

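### The PEG is taken from routine care within a 2-month window, so who has a value may depend on pain; adding its three items to the study's own questionnaire would avoid this at little cost

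*Protocol*

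**What the plan says.** The Measures section of the protocol describes the PEG as a 3-item scale and gives its source: "The PEG was completed as part of the participant's regular clinical care". The next sentence sets the matching rule: "Assessments within 2 months of the primary PTSM outcome assessment were used for these analyses". The other outcomes in that section (pain self-efficacy, pain acceptance, perceived efficacy with physicians, treatment satisfaction) carry no such statement.

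Study Procedures ties the clinic's routine PainTracker questionnaires to appointments. For intake it says: "All new patients were asked to complete the online questionnaires 1 week before their scheduled appointment". For recruitment it says: "Those who were scheduled for a follow-up appointment at UW CPR and completed the follow-up PainTracker assessment were presented with a question" about interest in the study.

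The SAP lists pain intensity and interference among the secondary outcomes. It analyses them by GEE with group, time and their interaction, on all available data, and states that "adjustments were not made for missing data". Its closing paragraph compares study completion between groups, and completers with non-completers. It gives no count of PEG values.

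**The concern.** Whether a participant contributes a PEG at 3 or 6 months depends on whether routine care produced one in the window. That may well be related to current pain, which is what the PEG measures. Unweighted GEE is generally valid only when missingness does not depend on the outcome given the model's covariates, and here those are group and time alone.

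Equal selection in the two groups cannot be presumed. The groups were recruited in sequence without randomisation, and care was unrestricted in both. Only the intervention group received self-management coaching, with summaries passed to the clinic provider at the next visit. These features could change clinic contact in either direction.

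At stake is the group comparison for one secondary outcome. Nothing in the documents suggests that the primary outcome, pain self-efficacy, has the same source.

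**Working it through.** **1. The plan's own figures.** The SAP gives completion of 88% (n = 45) in controls and 77% (n = 37) in the intervention group, with N = 99. The only denominators that fit are 51 and 48: 45/51 = 88.2%, 37/48 = 77.1%, 51 + 48 = 99. Non-completers are 6 + 11 = 17. The difference is non-significant, as stated: Pearson chi-square p = 0.14, Fisher exact p = 0.19. These figures describe completion of the study. A completer could still lack a PEG, and a non-completer could have one.

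**2. Selection model (assumed).** Let PEG in SD units be X ~ N(0, 1), and let the chance that a value exists be p(X) = 1/(1 + exp(−a − bX)), with b = ln(odds ratio per SD). Solve for a so that the mean of p(X) equals the observed fraction. The shift in the observed mean is then E[X·p(X)]/E[p(X)], by numerical integration. The documents give neither the odds ratio nor the fraction, so both are ranges.

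| Fraction observed | Shift, OR 1.5 | Shift, OR 2.0 |
|---|---|---|
| 50% | 0.20 SD | 0.31 SD |
| 70% | 0.12 SD | 0.19 SD |
| 77% | 0.091 SD | 0.147 SD |
| 88% | 0.048 SD | 0.079 SD |
| 90% | 0.04 SD | 0.07 SD |

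**3. From shift to bias in the group difference.**
- *Both groups select with the same odds ratio, availability 77% versus 88%* (completion percentages borrowed for illustration): 0.091 − 0.048 = 0.043 SD at OR 1.5, and 0.147 − 0.079 = 0.068 SD at OR 2.0. The net bias is about 0.04 to 0.07 SD.
- *Extreme case, pain drives availability in one group only:* the whole shift is bias, so 0.12 to 0.19 SD at 70% observed in that group, or 0.20 to 0.31 SD at 50%.
- *Same odds ratio and same availability:* the shifts cancel.

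**4. Scale.** The standard error of a simple two-group difference with the completers is √(1/45 + 1/37) = 0.22 SD. The central bias is therefore well under one standard error. The extreme case at 50% observed approaches or exceeds it, although fewer values would also make the standard error larger.

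**5. Precision.** The detectable difference at 80% power, two-sided 0.05, is (1.96 + 0.84) × √(1/n₁ + 1/n₂). With 45 and 37 it is 0.62 SD. If only 50% of each group had a PEG (25.5 and 24), it would be 0.80 SD.

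**6. The window.** The protocol does not state its direction. Read as plus or minus 2 months around each assessment, the windows are −2 to 2, 1 to 5 and 4 to 8 months. Adjacent windows share 1 month (1 to 2, and 4 to 5), so one PEG could serve two time points. No assignment rule is given.

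**The case against.** Taking the PEG from routine care is a defensible economy in a pilot with an acknowledged limit on budget and time. Several stronger readings are tempting, and the documents do not support them.

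- *That the PEG sample was smaller than for other outcomes.* No PEG count is given. A window of plus or minus 2 months is wide, and the patients were early in treatment, so availability may have been high.
- *That self-managing patients attended less, so the intervention group's PEG is biased upward.* Attendance by group is not reported, and passing coaching summaries to the provider could equally sustain clinic contact.
- *That the PEG was part of PainTracker.* Neither document says so. The 1-week rule describes new-patient intake, and the follow-up PainTracker assessment is mentioned only to explain recruitment. Those questionnaires were also completed online before the appointment, so attendance alone would not be the filter.
- *That the bias is as large as the one-group-only case.* That case is an extreme. The calculation also treats a single cross-sectional mean, whereas the SAP tests Group × Time, from which selection that is stable over time would partly cancel.

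These objections limit the size and certainty of the problem. They leave the source of the PEG, the window, the absence of any missing-data adjustment and the silence on PEG availability as they are. Figure 1 is not shown in the text available here and may contain assessment timing.

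**Conclusion.** The point holds in conditional form, as a cheap improvement. The PEG alone is described as coming from routine care, and participants without a routine assessment in the window have no value at that time point. This is mainly an issue at 3 and 6 months: enrolment followed a completed follow-up PainTracker assessment, so baseline is probably near complete if the PEG was part of it.

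The comparison is biased if availability depends on pain differently by group. The likely size is small: 0.04 to 0.07 SD with like selection and 77% versus 88% availability. It reaches 0.12 to 0.31 SD only if selection on pain operates in one group and 50% to 70% of that group is observed. All of these rest on an assumed logistic link and assumed availability. The direction is open. A reader might infer that the pain result is known to be distorted, but without PEG counts the documents cannot show that.

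**What to change.** **For a successor study:** administer the 3-item PEG with the study's own questionnaires at baseline, 3 and 6 months, and analyse those values. Keep the routine-care PEG as a sensitivity analysis. This gives the PEG the same timing as the other outcomes and removes both the clinic-timing selection and the window overlap. The cost is three 0–10 items per assessment in a battery for which participants are already compensated, with slight duplication for those who also complete the PEG in clinic. Study dropout (17 of 99) would remain.

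**For the data already collected:**
- report the number of PEG values and their lag from the study assessment, by group and time point;
- assign each PEG to one time point only, the nearest;
- compare participants with and without a PEG at 3 and 6 months;
- interpret the PEG result as supportive.

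This needs only tabulation and a rerun of one model.

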Official Study Title: PainTracker Self-Manager: a Web-based Platform to Promote and Track Chronic Pain Self-Management

NCT Number:	NCT03045081
Document Type:	Statistical Analysis Plan
Document Date:	March 21, 2018 (date of most recent submission/review by Journal of Pain)

Statistical Analysis Plan

Data were analyzed using SPSS version 25 (IBM Corp, Armonk, NY).

Descriptive statistics and frequency distributions were calculated for sample characteristics. Independent samples t-tests for continuous variables and χ^2 tests for categorical variables were used to evaluate for differences in demographic and clinical characteristics between the control and intervention groups. Given no statistically significant differences in demographic and clinical characteristics between the groups, the subsequent analyses (described below) did not adjust for any of these characteristics. A *P* value of <.05 was considered statistically significant. For all levels of analyses, adjustments were not made for missing data (i.e., no data imputations were performed).

Generalized estimating equations (GEE) were used to evaluate the effect of the intervention on primary (pain self-efficacy) and secondary (chronic pain acceptance, perceived efficacy in patient-provider interactions, pain intensity and interference, satisfaction with pain treatment) outcomes. GEE is an extension of generalized linear models that allows for the analysis of repeated measures with unknown covariance structure. GEE uses any and all available data that participants provide, even if follow-up data are missing (ie, intent-to-treat analysis). For all models, the main effect of

group and time, and the Group × Time interaction were evaluated. For this pilot study, Wald χ^2 statistics with *P* values <.05 for overall model effects were considered statistically significant. For models with significant Group × Time interactions, the main effects of group or time were not reported. For models with only a significant main effect of time, models were rerun without the interaction term to obtain the more accurate main effect.

Of note, there was no significant difference in the proportion of participants who completed the study (baseline, 3 months, 6 months) between the control (88%, n=45) and intervention (77%, n=37) groups. In addition, no significant differences in demographic characteristics or outcome measures were observed between participants who did (82%, n=82) and did not (17%, n=17) complete the study. Therefore, GEE models for (1) the entire study sample (N=99) and for (2) study completers (N=82) were evaluated.

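### Incomplete follow-up goes into GEE with no named working correlation or missing-data assumption, and two weak dropout comparisons lead into N=99 and N=82 models with neither named primary

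*SAP*

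**What the plan says.** The SAP's paragraph on models opens: "Generalized estimating equations (GEE) were used to evaluate the effect of the intervention on primary (pain self-efficacy) and secondary" outcomes. On the correlation between visits it says only that GEE "allows for the analysis of repeated measures with unknown covariance structure". No working correlation is named and no weights are mentioned. The same paragraph notes that GEE uses whatever data participants supply, and equates this with intent-to-treat. It sets P<.05 on Wald tests, which "for overall model effects were considered statistically significant". The paragraph before it says: "For all levels of analyses, adjustments were not made for missing data (i.e., no data imputations were performed".

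The last paragraph reports two comparisons. First, "there was no significant difference in the proportion of participants who completed the study" (control 88%, n=45; intervention 77%, n=37). Second, "no significant differences in demographic characteristics or outcome measures were observed between participants who did" (n=82) and did not (n=17) complete. It continues: "Therefore, GEE models for (1) the entire study sample (N=99) and for (2) study completers (N=82) were evaluated".

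Neither document states a missing-data assumption, says which model is primary, or gives missing visits by group and outcome. For the PEG, which came from routine care, the Protocol (Measures) adds: "Assessments within 2 months of the primary PTSM outcome assessment were used for these analyses".

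**The concern.** Unweighted GEE in general needs data missing completely at random. If dropout depends on scores already observed, the N=99 estimate depends on the working correlation, which a reader cannot find. The completer model can then be biased as well. With complete data and a full Group × Time model the working correlation does not change the group-by-visit means, so that omission matters for N=99 only.

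The only evidence offered about dropout is two non-significant results, joined to the two models by *Therefore*. In samples this small, non-significance says little about whether those who left resemble those who stayed. At stake is the 6-month difference in change, including that for the primary outcome, and how far a reader can rely on either fit.

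**Working it through.** **1. The plan's own figure.** 45 is 88% only of 51, and 37 is 77% only of 48; 51 + 48 = 99. Chi-square = 99 × (45×11 − 6×37)² / (51×48×82×17) = 99 × 273² / 3,412,512 = 2.16, P=0.14 (Fisher P=0.19). The reported non-significance reproduces.

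**2. The difference and its interval.** Non-completion is 6/51 = 11.8% and 11/48 = 22.9%, a difference of 11.2 points. SE = √(0.1176×0.8824/51 + 0.2292×0.7708/48) = 0.0756. The 95% CI is 0.1115 ± 1.96×0.0756, or -3.7 to 26.0 points.

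**3. What 17 versus 82 can detect.** The gap with 80% power is about (1.960+0.842) × √(1/17+1/82) = 2.802 × 0.2665 = 0.747 SD; by noncentral t it is 0.754 SD. If dropout in both groups depends on baseline score with log-odds 0.5 or 1 per SD worse, non-completers start 0.47 or 0.85 SD lower. This comparison finds those gaps 42% or 88% of the time. So it speaks against strong dependence on baseline, but not against moderate dependence.

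**4. Bias in the 6-month difference in change, with no true effect.** The documents give no SD, correlations or mechanism, so all of these are assumed:
- log-odds of dropout 0.5 or 1 per SD worse;
- dropout of 11.8% and 22.9%;
- correlations (baseline–month 3, months 3–6, baseline–month 6) of 0.6/0.6/0.6, 0.7/0.7/0.5 or 0.6/0.8/0.5;
- missing pattern: both follow-ups, or equal thirds (both, month 6 only, month 3 only). For dropout on the 3-month score, month 6 only.

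The largest values can be checked by hand. Let g be the mean score driving dropout among those who stay, minus its mean among all. For a standard normal score x with logistic dropout probability p(x) averaging π, g = −E[x·p(x)]/(1−π). At log-odds 1, numerical integration gives g = 0.106 (control) and 0.197 (intervention).
- Independence GEE with the full interaction takes the raw mean of those seen at each visit. Its bias is r(g_T − g_C), or r·g_T if only the intervention group depends on score. For dropout on the 3-month score with r=0.8: 0.8 × 0.091 = 0.07, or 0.8 × 0.197 = 0.16.
- Completers lose the same people at baseline too, so the shift is −(1−r)g. For dropout on the baseline score with r=0.5: −0.5 × 0.091 = about −0.05, or −0.5 × 0.197 = −0.10.

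Simulation with 400,000 per group gives the full ranges, in SD, when worse patients leave:

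| Dropout depends on | Groups affected | Independence GEE | Exchangeable GEE | Mixed model | Completers |
|---|---|---|---|---|---|
| Baseline score | both alike | +0.02 to +0.06 | -0.01 to 0.00 | 0.00 | -0.02 to -0.05 |
| 3-month score | both alike | +0.03 to +0.07 | 0.00 to +0.02 | 0.00 | 0.00 to +0.02 |
| Unseen 6-month score | both alike | +0.03 to +0.09 | +0.02 to +0.06 | +0.02 to +0.07 | +0.02 to +0.05 |
| Baseline score | intervention only | +0.03 to +0.12 | -0.02 to 0.00 | 0.00 | -0.04 to -0.10 |
| 3-month score | intervention only | +0.07 to +0.16 | 0.00 to +0.04 | 0.00 | 0.00 to +0.04 |
| Unseen 6-month score | intervention only | +0.07 to +0.20 | +0.04 to +0.14 | +0.04 to +0.15 | +0.04 to +0.10 |

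If better patients leave, all signs reverse. Some of the 17 may have missed only month 3, so month-6 loss may be smaller than 6 and 11.

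**5. Scale.** The standard error with full data is √(2(1−r)) × √(1/51+1/48): 0.180 SD at r=0.6 and 0.201 SD at r=0.5. With 45 and 37 seen at month 6 (r=0.6; r=0.5) it is 0.203; 0.222 for independence GEE, 0.195; 0.217 for the mixed model, and 0.198; 0.222 for completers.

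**The case against.** The strongest defence has five parts.

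- *The no-imputation sentence is not a defect.* This stands. A mixed model imputes nothing either, so the sentence would remain true after the fix, and the N=99 GEE does use partial data.
- *N=99 is already the lead.* This stands in part. The intent-to-treat label and the order of listing both point that way. What is missing is a sentence that says so.
- *The SAP never claims that missingness is ignorable.* True. The two fits can be read as a main analysis and a completer check. But the two P values are all that the SAP offers about dropout, and they carry little information.
- *The bias is small and hypothetical, and exchangeable GEE would nearly remove it.* Largely right. The SAP may have used such a structure; it does not say.
- *This is a pilot, already completed.* True, but the SAP still applies a P<.05 rule, and re-fitting needs no new data.

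A reader might also infer harm from the fact that two such fits can fall on opposite sides of .05. That is not evidence of bias. Under purely random dropout, reasonable analyses with moderate power often disagree near the threshold. In simulation with assumed effects of 0.3 and 0.5 SD, the mixed model and the completer model disagreed in 6–10% of trials, so the fix would not remove this.

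**Conclusion.** The concern holds as a gap in specification of minor to moderate weight. The working correlation and the missing-data assumption are unstated, the primary model is implied rather than named, and the dropout comparisons are too weak to support much.

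If dropout depends on observed scores, bias reaches about 0.07 SD (independence GEE) or 0.05 SD (completers) with both groups alike, and about 0.16 or 0.10 SD if only the intervention group is affected. It is at most about 0.04 SD for exchangeable GEE and about 0 for a mixed model. The standard error is about 0.2 SD. These sizes rest on the assumed scenarios above.

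Two stronger readings are not supported. A reader might infer that the reported results are biased; the documents show no mechanism, size or direction, and nothing in them shows dropout depending on scores in one group only. A reader might also infer that a significant result in either model was allowed to count; the SAP does not say so.

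**What to change.** Name the N=99 analysis as the single primary one. Fit it as a likelihood-based linear mixed model over baseline, 3 and 6 months (Group, Time, Group × Time, unstructured covariance, small-sample degrees of freedom) under a stated missing-at-random assumption. Nearly as good is GEE with a named non-independence working correlation.

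Label the completer model supplementary. Replace the *Therefore* step with 22.9% versus 11.8%, difference 11.2 points (95% CI -3.7 to 26.0). Report missing visits by group and outcome; for the PEG, study completion need not describe what is missing.

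Optionally, add a delta-adjusted sensitivity analysis that varies the shift in each group separately and together, since neither recommended model covers dropout on unseen scores.

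The cost is some re-analysis of data already held and intervals about 1–2% wider from small-sample degrees of freedom. The mixed model's standard error is no larger than that of independence GEE or completers. Because both documents report finished work, the changes must be labelled post hoc.
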